11.0 Data Quality and Performance Management

11.1 Site Training

Prior to study initiation and enrollment, all clinicians and staff who will be recruiting patients with recurrent high-grade NMIBC and their caregivers will complete study-specific training; a training log will be kept locally at each participating site.

The CCC will be responsible for maintaining administrative, clinical, and operational coordination for all aspects of the study. All site training and operational activities will be monitored and coordinated through the CCC. This includes training of research coordinators and site leaders, maintenance of data abstraction quality, and completeness of data.

11.2 Quality Management Plan

The quality management plan (QMP) will include verification that sites have appropriately met the requirements to assure quality of all study-related activities. Each site will be responsible for maintaining accurate and complete patient charts and informed consent documentation. The QMP is in place to verify good practice.

The CCC and DCC will regularly review participant enrollment, reasons for exclusion, participant demographics, and follow-up rates by site in order to assess proximity to enrollment targets, site performance, and protocol adherence.

The DCC will set up in-line data quality checks within the data entry system, which will check for missing information, inconsistencies, and logic errors. The CCC and DCC will monitor this information on a regular basis. In addition, the DCC will perform quality assurance checks by running regular data quality reports. These reports include missing values for required fields, incorrect data type, range checks, outliers, hidden fields that contain values, and multiple-choice fields with invalid values. Values that need to be corrected will be brought to the attention of the research staff at that site. The DCC and CCC will investigate any discrepancies or unexpected values that were discovered through the regular report or through visual inspection.

Research staff from the CCC will be responsible for regular remote monitoring of each site. This will include review of participant enrollment forms, patient reported outcomes data entry, EMR data abstraction, and any AEs or SAEs. Source documentation may be uploaded in designated REDCap fields. Regular meetings with the research site leads at each site will be held via phone to relay any concerns or walk through issues. Retraining will be available through the CCC if needed.

For sites that are found to have several inconsistencies and errors in data quality and completeness, or an increased number of protocol deviations compared to other sites, monitoring visits will be scheduled and conducted as needed.

11.3 Performance Management Plan

Site study leadership teams will review enrollment rates and any outstanding needs or concerns with the CCC on a regular basis. The purpose of these individual site meetings is to monitor site progress against anticipated and expected site enrollment targets. If screening/recruitment goals are not being met, the CCC will implement the following Performance Management Plan, consisting of:

1. Site Progress Call to review and discuss:
 - i. Site specific screening and enrollment rates
 - ii. Missed participants, study refusals
 - iii. EMR abstraction completion rates
 - iv. Statement of work and milestones review
 - v. Support or training needs for the site from the CCC
 - vi. Plan of action to address enrollment shortfalls
2. Interval Check-In Call:
 - i. Site specific screening
 - ii. Plan of action results
3. Follow-up Call(s) as needed:
 - i. Continued training
 - ii. In-person site visit (as needed)

Site performance will be monitored on a regular basis by the CCC and concerns will be elevated to the CISTO Executive Committee. If a site consistently fails to meet expectations in comparison to the average study site, suspension or termination of the site subcontract may be necessary.

11.4 Protocol Violations

A protocol violation is any non-compliance with the clinical trial protocol or Good Clinical Practices. The noncompliance may be either on the part of the participant, the investigator, or the study site staff and most often is related to study enrollment. Anticipated protocol violations are 1) Participant enrolled but did not meet inclusion criteria, 2) Participant enrolled but exclusion criteria present, 3) Consent not obtained in accordance with IRB guidelines. Participants enrolled and later found to be ineligible may be followed depending on information available at enrollment.

All violations from the protocol will be addressed in study participant source documents. A record of the violation will be maintained in the regulatory file, as well as in the participant's study chart. Protocol

violations will be sent to the local IRB per their guidelines. The site investigator/study staff will be responsible for knowing and adhering to their IRB requirements.

12.0 Protection of Human Participants

Prisoners will be excluded from CISTO study participation.

The primary risks of this study are loss of patient privacy, loss of confidentiality, and study burden. Loss of confidentiality could occur if the study database were breached. This risk will be low as a result of numerous steps to protect confidentiality. Approaching patients about enrollment in the clinic poses a risk to privacy. We anticipate this risk to be low. Patients will be approached in a private clinic room. To avoid threats of coercion, providers will be educated but not directly involved with recruitment of participants. All participants may be at higher risk for psychological discomfort or anxiety due to perceived or actual additional burdens related to study participation. Questions about quality of life and bothersome symptoms may be uncomfortable for some participants, but are also part of standard of care during many routine clinic visits. Thus, we expect the risks of discomfort or anxiety related to study procedures to be low. It is unlikely there will be direct, short-term benefits to individual participants in this study. The long-term benefit arises from the potential to improve decision-making for patients deciding on treatment following a diagnosis of recurrent high-grade bladder cancer.

Informed consent is a process that is initiated prior to the individual's agreeing to participate in the study and continuing throughout the individual's study participation. Extensive discussion of risks and possible benefits of both treatment options will be provided to the participants using standardized materials, which can include an informational video. Consent forms describing in detail the study procedures and risks will be given to the participant and documentation of informed consent will be required prior to completing study assessments.

Consent forms will be IRB-approved and the participant will be given sufficient time to read and review the document and discuss with their caregiver, family member, friend, or legal representative. If they require assistance to reach their caregiver, family member, friend, or legal representative, such as the use of a telephone, that will be facilitated. After this, they will be specifically asked if they have any questions or concerns, which will be addressed, or would like more time to consider their participation, which will also be provided. The study investigator or coordinator will explain the research study to the participant and answer any questions that may arise. The participants will sign the informed consent prior to completing any study related activities. The participants may withdraw consent at any time throughout the course of the study. A copy of the informed consent will be given to the participants for their records. The rights and welfare of the participants will be protected by emphasizing to them that they will still be able to receive medical care at the facility if they decline to participate in this study.

Participant confidentiality is strictly held in trust by the participating investigators and their staff.

13.0 Ancillary Studies

An ancillary study subcommittee within the CCC will work with interested investigators, representatives of PCORI and CISTO stakeholders to coordinate, seek funding for, facilitate and plan ancillary studies that may be linked to the CISTO trial.

## 1. General Design Considerations

### 1.1 Aims and Hypotheses

**Aim 1:** To compare patient-reported and patient-centered clinical outcomes between patients undergoing radical cystectomy and those receiving bladder-sparing therapies (BST) for NMIBC that have failed first-line BCG.

*Hypothesis 1.1: Patients undergoing radical cystectomy will have worse generic health-related QOL within 12 months of bladder removal surgery compared with BST patients.*

*Hypothesis 1.2: 12-month disease-free survival and metastasis-free survival will be better among radical cystectomy patients than among BST patients.*

*Hypothesis 1.3: Patient-reported and clinical outcome differences will vary within important subgroups including women, non-white patients, elderly patients, patients with multiple comorbid health conditions, patients with poor urinary function scores at the time of BCG failure, patients without caregivers, patients with atypical cancer histologies, and patients receiving investigational agents.*

**Aim 2:** To characterize the heterogeneity of treatments received and corresponding patient and caregiver preferences for NMIBC that have failed first-line BCG.

*Hypothesis 2.1: Patients who choose radical cystectomy for NMIBC with BCG failure will do so more often because they feel this offers their best chance for survival. Patients who choose BST will do so more often because they are concerned about the complications and QOL detriments associated with radical cystectomy.*

*Hypothesis 2.2: Patient and caregiver preferences will correlate strongly with observed treatments received and health-related QOL outcomes. We anticipate that QOL will vary by concordance of treatments received with treatment preferences and health state utilities.*

### 1.2 Design

The CISTO Study is a pragmatic, prospective observational cohort study of patients with recurrent high-grade NMIBC who have selected management with BST or radical cystectomy. This multicenter study has an allocation ratio of 2:1 across treatment arms (BST to radical cystectomy, respectively) by site. A prospective observational cohort study design was chosen for the CISTO Study in response to critical input from the BCAN Patient Survey Network. Among 291 respondents with NMIBC, only 11% reported being willing to consent to randomization for a study of BST versus radical cystectomy. Therefore, a prospective observational cohort study was selected as the highest quality study design for addressing the research questions.

### 1.3 Treatment Group Selection

Patients are enrolled in either of two arms, based on the patient's individual treatment decision: participants undergoing radical cystectomy (any surgical approach including open or robotic surgery) and those receiving BST (additional BST, including BCG, or intravenous immunotherapy) for recurrent high-grade NMIBC.

## 1.4 Enrollment Timing

A participant's study clock begins on the date of completion of the baseline survey entry date.

## 1.5 Analyses

Primary analyses will be based on an Intention to Treat (ITT) approach. Patient data will be analyzed according to the treatment arm decided upon at enrollment regardless of whether that treatment was initiated. Due to the 2:1 allocation of treatment, statisticians and analysts are not blinded to the study treatment assignment when conducting statistical analyses. Patients that withdraw consent after enrollment and before the beginning treatment will be excluded from the ITT analyses. Patients will also be excluded from the study cohort if found to meet exclusion criteria upon review of EMR data entered into the study data management system.

## 1.6 Analysis Timing

To facilitate and expedite publication of the primary results within the allotted window of funding for CISTO, an analytic data set will be frozen on March 14, 2024. All baseline information will be included in the analytic data set, as well as all longitudinal follow-up data for patients were enrolled in CISTO on February 14, 2023 or earlier. Statistical analysis, tables, and figures will be generated by the data coordinating center and manuscript development will begin in conjunction with the CISTO Writing Committee who are not involved with patient care or outcome collection. Once data have been collected and cleaned for the final participant (estimated January 2025), a final analytic data set will be generated to refresh tables, figures, and associated details with reporting.

## 2. Primary Outcome

The *primary outcome* is patient-reported health-related quality of life as measured with the EORTC QLQ-C30, which has been previously used in bladder cancer populations. The *primary endpoint* is the physical functioning domain score of the EORTC QLQ-C30 at 12-months.

## 3. Secondary Outcomes

For patients, secondary outcomes through 12 months include self-reported urinary, bowel, and sexual function and bothersomeness as measured with the Bladder Cancer Index, PROMIS depression and anxiety, EuroQoL 5D, NMIBC treatment preferences, decisional regret, financial distress measured with the Comprehensive Score for Financial Toxicity (COST), healthcare utilization measured as 12-month hospital and urology clinic days, return to work/normal activities, 12-month cancer-specific survival, metastasis-free survival, bladder cancer-specific survival, and progression to muscle-invasive bladder cancer. Among patients with available data, we will assess health-related quality of life, health literacy, urinary function, sexual function, financial distress, healthcare utilization, disease-free and metastasis-free survival, bladder cancer-specific survival, and progression at up to 48 months, and up to 6 additional years for extended follow-up.

## 4. Data Analyses

We will use descriptive statistics to characterize the treatments received, PROs, and clinical outcomes. Prior to statistical analysis, we will first compare continuous demographic and clinical characteristics by treatment group with Wilcoxon rank-sum tests to protect against violations of normality assumptions. P-values from Exact Conditional Tests, such as Fisher's exact test and its multi-degree of freedom extensions, will be used to compare categorical data.

To address treatment selection bias and potential confounding by indication in the comparison of BST vs. radical cystectomy, we will utilize targeted maximum likelihood estimation (TMLE) as the primary analytic approach for causal effect estimation using observational data. Unlike approaches that focus on creating

carefully matched treatment and control groups, TMLE allows for the inclusion of all patient participants and their reported outcome measures. TMLE first uses covariate-adjusted regression models to generate an initial estimate of the treatment effect of radical cystectomy through the creation of *potential outcomes*: two predicted outcomes for each individual patient participant, under the hypothetical assumption that they had been treated with either radical cystectomy or BST. Next, as with a propensity score approach, we will estimate the probability of treatment with radical cystectomy using SuperLearner. The SuperLearner procedure selects the best weighted combination of prediction models from among candidate learners such as logistic regression, stepwise logistic regression, generalized additive models, Bayesian GLM, LASSO, random forest, gradient descent boosting, support vector machine, and the sample mean. Finally, we will use the probabilities obtained in the second step to update the initial estimate of each patient participant's pair of potential outcomes and the TMLE estimate is interpreted as the difference in outcomes if all patients had been treated with BST versus having been treated with radical cystectomy.

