9.4 Sample Size and Statistical Power

We aim to recruit from a heterogeneous patient population that will allow for rich and broadly applicable estimation of outcomes and experiences after NMIBC that recurs after first-line BCG. **We will enroll up to 900 participants across a broad geographic recruitment area.** This cohort would represent the largest pragmatic study of recurrent high-grade NMIBC patients to date. The total sample size for CISTO is primarily motivated by statistical power considerations for **Aim 1**, comparing QOL between patients treated with medical management versus radical cystectomy. Presently, there are no guiding documents

on directly using TMLE in the calculation of statistical power for designing an observational study. The variance of the treatment effect estimate—and thus power—is a complicated function of the number treated in each group, the potential and observed outcomes, and the covariate-based probabilities of treatment with radical cystectomy. The 2:1 recruitment ratio of medical management to radical cystectomy patients at each CISTO site will ensure at least a 33% rate of radical cystectomy in the CISTO study population. However, based on actual rates of enrollment of cystectomy patients, we motivated the study sample size of 572 using 40.9% cystectomy patients in a standard two-sample repeated measures approach that will be less efficient than the analytic methods used at the time of data analysis.

Statistical power was fixed at 0.80 throughout and we considered two-sided tests with alpha=0.05 indicating statistical significance, with no adjustment for multiple comparisons for the primary question of interest. Correlation between repeated measures was assumed to be 0.3, an estimate we have observed in numerous other QOL studies. Minimal detectable effect sizes (units of QOL standard deviation) are reported in **Table 3** below for Aim 1 within subgroups with varying prevalence.

Table 3. Minimal Detectable Effect Sizes

		Subgroups		
		50%	30%	20%
Aim 1: Patient QOL	Overall	0.24	0.34	0.44

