Aim 2 is largely descriptive in nature and no statements of statistical power were considered. With recruitment of 572 patient participants, anticipating 235 radical cystectomy patients and 337 patients treated with medical management in Aim 1 and conservatively allowing for 10% missing data, this study has >0.80 statistical power to detect small differences in QOL between treatment approaches (Cohen's $d = 0.24$)²⁰ that are well below the minimally important difference of 0.5. Assuming a similar balance of treatments within subgroups, this study has >0.80 power to detect moderate but clinically important effect sizes (Cohen's $d = 0.43$) within subgroups as small as 30% of the study cohort. From SEER, large treatment effect differences would be detectable in subgroups of gender (20% female), age (52% over 75), comorbid health conditions (22% Charlson Index 1 or greater), and CIS (25%). We will plan a subgroup analysis for patients receiving investigational agents as part of a phase III clinical trial if at least 10% of participants in the medical management arm are in a trial. To inform power calculations for our secondary outcomes of bladder cancer-specific mortality, we used data from a microsimulation model demonstrating low anticipated 1-year mortality event rates (0.8% for radical cystectomy, 3.6% for continued medical management). We would have 69% power to detect a similar difference in one-year mortality due to bladder cancer and 80% power to evaluate the difference between study arms in 2-year bladder cancer-specific mortality.

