### 5.3 Handling

In final manuscripts and analyses, the number of non-responders will be enumerated by study arm according to CONSORT guidelines. We will conduct a missing data analysis to describe and characterize enrolled participants who do not provide further response due to *attrition* or *dropout*. As a part of treatment effect estimation, the TMLE algorithm provides an integrated approach to incorporating uncertainty that arises due to missing longitudinal data. The mean outcome conditional on observing the outcome may be a biased estimate when missingness is informative. TMLE can reduce this bias when missingness is a function of measured baseline demographic and clinical characteristics. Missing outcome measurements will be accounted for by nonparametrically estimating the missing data mechanism to produce a matrix of missing data probabilities conditioned on baseline demographic and clinical characteristics. The missing data conditional probabilities will then be incorporated into the TMLE estimation procedure during the third step of updating potential outcomes.

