## 6. Sample Size and Accrual

With recruitment of 572 participants, this study has  $>0.80$  statistical power to detect small differences in QOL between treatment approaches (Cohen's  $d = 0.24$ , or 5.5 points on the physical function scale of EORTC-QLQ-C30). Power analyses conservatively allowed for 10% missing data and assumed a correlation between repeated QOL measurements of 0.3. Assuming a similar balance of treatments within subgroups, this study also has  $>0.80$  power to detect moderate but clinically important treatment effects (Cohen's  $d = 0.43$ , or 9.9 points on the physical function scale of EORTC-QLQ-C30) within subgroups as small as 30% of the study cohort. Anticipated subgroups of this size include patients aged 75 years or older, women, and patients with multiple comorbid health conditions. For the secondary outcome of bladder cancer-specific mortality, data from a review combining multiple trials demonstrated an anticipated 1-year bladder cancer-specific mortality rate of 4.8% when treated with medical management. Assuming a 4.8% mortality rate in the medical management arm, this study has power to detect differences in 1-year bladder cancer-specific mortality rates of  $\leq 1\%$  in the radical cystectomy arm (power  $> 80\%$ ).

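### The SAP does not specify cross-fitting for the SuperLearner propensity and nonparametric missingness models in TMLE; fitted in-sample, they can make the confidence interval too narrow

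*SAP*

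**What the plan says.** SAP section 4 states that "we will utilize targeted maximum likelihood estimation (TMLE) as the primary analytic approach for causal effect estimation using observational data". It describes three steps.

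1. Outcome model: "TMLE first uses covariate-adjusted regression models to generate an initial estimate of the treatment effect of radical cystectomy".
2. Treatment model: "we will estimate the probability of treatment with radical cystectomy using SuperLearner". The learners are given as examples. They include parametric and additive models as well as "LASSO, random forest, gradient descent boosting, support vector machine, and the sample mean".
3. Update: the probabilities from step 2 are used to revise each patient's pair of potential outcomes.

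SAP section 5.3 handles missing outcomes by "nonparametrically estimating the missing data mechanism to produce a matrix of missing data probabilities", and these probabilities enter the same update.

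Protocol section 9.4 sizes the study at 572, "anticipating 235 radical cystectomy patients and 337 patients treated with medical management in Aim 1", with 10% missing data allowed for. On significance it says that "we considered two-sided tests with alpha=0.05 indicating statistical significance".

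Neither document mentions cross-fitting, sample splitting, number of folds, a bound on the propensities, learner tuning, or a variance estimator for TMLE.

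**The concern.** SuperLearner uses cross-validation to choose the weights of its learners. In the usual implementation the learners are then refitted on all patients, and the fitted probabilities for those same patients are passed on. A random forest or boosted model predicts its own training data too well, so the probability assigned to the treatment a patient actually chose is pulled upwards. The inverse weights in the TMLE update become too small, and so does the influence-curve SE computed from them. The real sampling variation of the estimate does not shrink with it. A flexible missingness model can do the same through its own inverse weights.

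At stake are the width of the confidence interval and the false-positive rate of every TMLE comparison, including physical functioning at 12 months. The choice is also open to analysts who, under SAP section 1.5, are not blinded to treatment.

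**Working it through.** **The plan's own figure.** Inputs from Protocol 9.4: 235 and 337 patients, 10% missing, correlation 0.3, two-sided alpha 0.05, power 0.80.

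- Evaluable: 235 × 0.9 = 211.5 and 337 × 0.9 = 303.3, about 515 in total.
- Detectable effect = (1.960 + 0.842) × √(1/211.5 + 1/303.3) × √(1 − 0.3²) = 2.802 × 0.0896 × 0.954 = 0.239.

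This matches the stated 0.24. The figure comes from a two-sample repeated-measures calculation, so it does not depend on how TMLE is fitted.

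**Main simulation.** The data-generating assumptions are not in the documents. There were 250 data sets with n = 572, 41% treated, 12 covariates, a linear outcome regression that was deliberately imperfect, a bounded-outcome TMLE update and an influence-curve SE. A plain logistic propensity did not capture the treatment choice: its TMLE was biased by about 1.8 points. The SuperLearner library was logistic, LASSO, random forest, boosting, SVM and the mean.

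| Propensity | Mean probability of treatment received | Mean SE | Empirical SD | SE/SD |
|---|---|---|---|---|
| True | 0.58 | 1.64 | 1.66 | 0.98 |
| Logistic, in-sample | 0.57 | 1.62 | 1.70 | 0.95 |
| SuperLearner, in-sample | 0.61 | 1.35 | 1.67 | 0.81 |
| SuperLearner, out-of-fold | 0.56 | 1.55 | 1.68 | 0.93 |
| Random forest alone, in-sample | 0.83 | 0.88 | 1.72 | 0.51 |
| Random forest alone, out-of-fold | 0.55 | 1.70 | 1.72 | 0.98 |

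Ratios are from unrounded values, with Monte Carlo error of about 4 to 5%. Half-widths are 1.96 × 1.35 = 2.65 and 1.96 × 1.55 = 3.04 points, so the in-sample interval is 13% narrower (equivalently, the out-of-fold interval is 15% wider). This happened although random forest and boosting together received only about 14% of the weight.

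The out-of-fold version reused the SuperLearner weights from the same folds. A fully nested run of 20 data sets gave the same direction (mean SE 1.35 against 1.58).

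**Conversion to error rate.** For an otherwise unbiased estimator, two-sided error = 2 × [1 − Φ(1.96 × ratio)].

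| SE/SD | 0.75 | 0.81 | 0.87 | 0.93 | 1.00 |
|---|---|---|---|---|---|
| Error | 0.14 | 0.11 | 0.09 | 0.07 | 0.05 |

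**Sensitivity to the library and to the form of treatment choice** (further simulations, also under assumed data):

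- Library with a spline GAM and LASSO added: 0.74 to 0.78 in-sample against 0.87 to 0.94 out-of-fold with non-linear choice; about 0.93 against 1.02 with linear choice.
- Additive non-linear choice, 80 data sets: with logistic, forest, boosting and the mean, the tree learners took 73% of the weight and the in-sample ratio was 0.76. Adding a spline GAM and LASSO cut that weight to 25% and raised the ratio to 0.87 (95% range about 0.73 to 1.01).
- Short library without GAM, LASSO or SVM, few data sets: 0.72 against 0.98 cross-fitted (42 sets, imperfect outcome model); 0.90 against 1.08 (54 sets, correct outcome model); about 1.0 in-sample with linear choice (28 sets). Mean SE with non-linear choice was 1.39 in-sample against 1.81 to 1.84 cross-fitted; 1.81/1.39 = 1.30.

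The direction is the same throughout. The size depends on how much weight the tree learners receive. The main simulation had no missing outcomes, so extending the point to SAP 5.3 rests on the mechanism and not on a figure.

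**The case against.** A reader might infer that the plan has decided against cross-fitting and that its primary interval is therefore too narrow. The documents do not support that: they are silent, and an analyst could cross-fit without departing from them. They also name no TMLE variance method, so the link to an influence-curve SE is an assumption about usual practice. The two-sided 0.05 in Protocol 9.4 is stated for the power calculation.

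A reader might also quote the worst ratio, 0.72, with an error of about 0.16. That comes from 42 data sets (95% range 0.56 to 0.88) and a library without the GAM, LASSO and SVM that the SAP lists. With those smoother learners available, SuperLearner gives the trees less weight and the shortfall is smaller. When treatment choice is close to linear, there is little or no problem.

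Other points on the plan's side:

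- The outcome step is described as covariate-adjusted regression, so a need to cross-fit it is not shown.
- SAP section 4.1 calls linear mixed models the primary approach for QOL trajectories, which clouds which interval is primary. SAP sections 4 and 4.4 and Protocol 9.2 nevertheless point to TMLE for the treatment comparison.
- SAP section 4.4 plans propensity matching and G-computation as checks. These give other intervals but do not correct the TMLE SE.

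These points limit the size of the effect and the certainty that it will occur. They do not remove it: applied in its usual form, the named method leaves the SE exposed.

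**Conclusion.** The point holds as a cheap improvement. Applied in the usual in-sample way at about 515 to 572 patients, with an influence-curve SE, the described method can understate the SE. The SE/SD ratio is roughly 0.75 to 0.87 if treatment choice is non-linear (two-sided error about 0.14 to 0.09), and about 0.92 to 1.0 if it is linear. Cross-fitting moves the ratio closer to 1, to about 0.87 to 1.08.

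These figures rest on assumed covariates, treatment mechanisms and learner tuning, and on modest numbers of data sets. The error rates also assume no residual confounding bias. In the main simulation, observed coverage was 78% in-sample and 86% out-of-fold, but both values also reflect a bias of about 1.4 points from the imperfect outcome model, which cross-fitting does not cure. The planned sample size and the stated detectable effect of 0.24 are unaffected.

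**What to change.** In SAP sections 4 and 5.3:

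- Specify cross-fitted TMLE, for example with 10 folds. The SuperLearner treatment model and the missingness model should be trained outside each patient's fold, and the outcome model too if it uses flexible learners.
- State the bound applied to the propensities.
- Take the SE from the cross-validated influence curve.

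The cost is SAP wording, computing time and a wider interval. The widening is about 9 to 30%, depending on the weight the tree learners receive: 15% in the main simulation, and about 30% in the short-library runs with non-linear choice. Some cross-fitted ratios reached 1.08, so mild over-coverage is possible. Data collection and sample size do not change. SAP section 1.6 plans a final refreshed data set, so the specification can be fixed at least for that analysis.
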